## 7.6.4 Data sharing

If necessary, aggregated data output from SAS scripts will be shared by data partners with the PHARMO Institute for further analyses and pooling.

The results are sent to PHARMO, using a secure file transfer protocol.

## 7.7 Data analysis

All analyses will be performed in collaboration between the PI, as the scientific lead, and the PHARMO Institute for Drug Outcomes Research, the coordinating center for this multi-database study. Data will be deposited in the Remote Research Environment and participating data partners can inspect the analysis by remotely accessing.

For Aarhus, HSD, SIDIAP, CPRD, and GePaRD SAS version 9.4 (SAS Institute Inc., Cary, North Carolina) is available for data processing and analysis. At ARS, R version 4.0.3 (R Foundation for Statistical Computing, Vienna, Austria) will be used for data processing and analyses. SAS programs will be used by data partners to generate aggregated data files to create interim reports. Since ARS does not have a SAS license, the ARS database used SAS programs shared by PHARMO to create transformation programs in R. These R programs will be compared with SAS programs by looking at the results using simulated data.

Linkage to hospital data (CPRD, SIDIAP, PHARMO) is used where feasible to supplement the basic datasets that include regular data available from the databases. In these databases, the study objectives will be assessed in the full population (with or without linkage), and – as a stratified analysis – in a subgroup of patients with linked hospital data (linked data is currently available for approximately 55% of the full CPRD population, about 33% of the population in SIDIAP, and about 75% of the population in PHARMO).

A detailed description of the analyses is provided in the SAP and has been updated along this protocol amendment.

### 7.7.1 Analyses timing

#### 7.7.1.1 Yearly analysis for interim reports

Interim reports will be submitted on a yearly basis with a first report using data until 31 Dec 2016. Data will be available in all databases with a delay of up to 12 months, i.e. Q2 2017 for data up to 31 Dec 2016 and 9 months in PHARMO (i.e. data up to 31 Dec in a given year available in Q3 of the following year). GePaRD has a data lag time of up to 2 years. The first interim report was submitted in Q1 2018. The last interim report is due in Q1 2022.

These interim reports will include the following information:

- Number of patients in the different exposure cohorts
- Patient exposure in the different exposure cohorts
- Baseline characteristics in terms of demographics, comorbidity, and concomitant medication use at the index date of the different exposure cohorts
- IRs with 95% CIs for the safety events of interest by week of use

Since validation takes time, validated IRs (for the primary safety event angioedema) will be made available for the final analysis.

### 7.7.1.2 Final analysis

The final analyses will be conducted at the end of the study with cumulative study data available at the time of data extraction around December 2021. The expected study period by database is presented earlier in [Table 7-1](#).

#### 7.7.1.2.1 Demographic and baseline characteristics of exposure cohorts

Demographic and baseline clinical characteristics of adult patients with HF initiating sacubitril/valsartan or ACEIs will be described, using contingency tables for categorical variables and mean, standard deviation (SD), range, median and interquartile range (IQR) for continuous variables in each database. Differences in demographic and baseline characteristics of adult patients with HF initiating either sacubitril/valsartan or using an ACEI will be assessed via standardized mean differences (SMD). A cross tabulation of age groups and sex will be provided for adult patients with HF initiating either sacubitril/valsartan or using an ACEI.

Information on cohort attrition will be provided in a study diagram and table. Treatment-related information (e.g. treatment duration, reason for discontinuation, switch/add-on therapy, etc.) will be summarized per treatment cohort.

In this context, we also aim at investigating the 36-hour washout period recommended in the SmPC of sacubitril/valsartan for patients previously using ACEI who started on sacubitril/valsartan in actual clinical care setting as requested by the PRAC. The current proposal is to assess the proportion of adult patients with HF initiating sacubitril/valsartan for whom there is evidence indicating concurrent use during the 36-hour period. This will be performed by assessing the proportion of sacubitril/valsartan users with concurrent prescriptions (or pharmacy fills) of ACEI (i.e. on the same day). Concurrent prescriptions (or pharmacy fills) are the only reliable indicator of non-adherence to the 36-hour washout period (see also [Section 7.10](#)).

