#### 7.1.1 Rationale for study design

To obtain a robust estimate of the incidence of angioedema – the primary safety event of interest – as well as of the other safety events (i.e. hypotension, hyperkalemia, hepatotoxicity, and renal impairment) in patients newly starting sacubitril/valsartan (incident users), an initial cohort of all sacubitril/valsartan initiators will be identified (regardless of prior exposure to ACEIs or ARBs) with patient accrual beginning at the specific launch date of sacubitril/valsartan (see [Table 7-1](#)) in those EU countries from which healthcare database information will be used for this study (see [Section 7.4](#) ‘Data sources’). In addition, an initial contemporaneous comparator cohort of ACEIs initiators will be identified. Data collection will end when the necessary sample size of 24,000 PYs is reached (see [Section 7.5](#) ‘Study size/power calculation’), but on 31 December 2021 at the latest (even when the target sample size is not reached).

A new user design ([Ray 2003](#), [Food and Drug Administration 2013](#), [Yoshida et al 2015](#)) is proposed to minimize the risk of a prevalent user bias and depletion of susceptibles. This is of particular importance for ACEIs users. Sacubitril/valsartan was newly introduced to the market and the cohort of users therefore automatically consists of new users. As indicated in the sacubitril/valsartan ‘Summary of Product Characteristics’ (SmPC), it is contraindicated for patients with a known history of angioedema related to previous ACEI or ARB therapy, or with hereditary or idiopathic angioedema. The combination of sacubitril/valsartan with an ACEI is contraindicated due to the increased risk of angioedema. Sacubitril/valsartan must not be initiated within 36 hours after taking the last dose of ACEI therapy.

Since the majority of sacubitril/valsartan users are expected to have been treated with an ACEI or ARB before starting sacubitril/valsartan, these patients will likely have a lower baseline risk of angioedema as susceptible patients have been depleted. ACEI initiators who are treatment

naïve to ACEIs and ARBs however, will likely have a higher baseline risk of angioedema since this population includes all patients who are susceptible to an angioedema event.

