### 7.9 Limitations of the research methods

The most important uncertainty is the use of sacubitril/valsartan, which may decrease the precision of the estimates from the study. We expect major issues with the number and selection of the sacubitril/valsartan and ACEI cohorts that are naïve to prior ACEI/ARB exposure. Difference between cohorts will be inspected by covariates (baseline characteristics) and a propensity score.

The limitations of this study will be mainly due to the availability and level of detail of data. Not all potential confounders (e.g. life style factors such as smoking, BMI) are contained in the databases, and not all variables contain the information in desired detail. We will be missing

information on race – which is an important risk factor and effect modifier for angioedema – in most databases. However, we will use available information on race (e.g. from CPRD) in a sensitivity analysis. Particularly, information on the prescribed dose and duration of a prescription is not contained in all databases and has to be estimated, which might lead to misclassification of exposure. None of the databases have data on actual drug intake. This implies that we do not know whether the patient actually took the drug. Assessment of the 36-hour washout period is therefore limited to determining concurrent prescriptions (or pharmacy fills) of ACEI and sacubitril/valsartan on the same day. As angioedema risk is higher if sacubitril/valsartan is started before the determined washout period from ACEI, the risk of angioedema in cohort 1 may be slightly overestimated.

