## 7.10 Other aspects

At the explicit request of the PRAC, Novartis committed to investigate the 36-hour washout period recommended in the SmPC of sacubitril/valsartan for patients previously using ACEI

and who started on sacubitril/valsartan in actual clinical care setting. This washout period should lower the potential risk of angioedema when a patient is exposed to both sorts of medicines at one time. Given the nature and limitations of database research, however, such a research question is difficult to operationalize. The MAH, Primary Investigator and Database Custodians have assessed how to optimally implement this research question and will report the concurrent prescriptions (i.e. on the same day) of ACEI and sacubitril/valsartan as violation of the recommended washout period.

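### The 36-hour washout proportion is posed for prior ACEI users but taken over all sacubitril/valsartan starters, so it probably understates the figure among switchers

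*Protocol*

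**What the plan says.** Section 7.1.1 gives the rule behind the measure: "Sacubitril/valsartan must not be initiated within 36 hours after taking the last dose of ACEI therapy". Section 7.7.1.2.1 says the washout will be investigated "for patients previously using ACEI who started on sacubitril/valsartan in actual clinical care setting as requested by the PRAC", and Section 7.10 states the same population. The operational measure in 7.7.1.2.1 is broader. The proposal is to "assess the proportion of adult patients with HF initiating sacubitril/valsartan for whom there is evidence indicating concurrent use during the 36-hour period", carried out as the "proportion of sacubitril/valsartan users with concurrent prescriptions (or pharmacy fills) of ACEI (i.e. on the same day".

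The reason given for same-day records is that "Concurrent prescriptions (or pharmacy fills) are the only reliable indicator of non-adherence to the 36-hour washout period". Section 7.9 explains that no database records actual intake and continues: "Assessment of the 36-hour washout period is therefore limited to determining concurrent prescriptions (or pharmacy fills) of ACEI and sacubitril/valsartan on the same day". Section 7.10 calls the question hard to put into operation and says the study partners "will report the concurrent prescriptions (i.e. on the same day) of ACEI and sacubitril/valsartan as violation of the recommended washout period".

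Three other places matter. The exclusion criteria in Section 7.2.4 remove patients with same-day records and say they will be reported. Section 7.3.1.1 defines cohort 2 as the starters with no ACEI or ARB in the 365 days before index, a subset of all starters. Section 7.3.3 lists ACEI use in the prior 365 days, with the index date left out, as a baseline variable separate from ARB use.

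**The concern.** The question and the measure refer to different populations within one paragraph. A washout can be kept or broken only by someone coming off an ACEI. Starters coming from an ARB, or from neither class, have no recent ACEI on record to wash out. Counting them pulls the proportion down without saying anything about how switches are managed.

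The output was requested by the regulator and concerns a co-exposure that the protocol links to higher angioedema risk. A low figure could be read as good adherence when part of it only reflects how many starters were never at issue. The same dilution would make databases with different shares of prior ACEI users look different even if switching practice were identical.

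The label is a second, smaller matter. Section 7.10 equates same-day records with violation of the washout, although Section 7.9 implies that some early starts are not caught by them.

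**Working it through.** The protocol gives no expected proportion, study size or precision for this output, so there is no figure of its own to reproduce. The check covers the direction and possible size of the dilution, and then the label.

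**Inputs**
- N = 29,000 expected starters (abstract, study size).
- s = share of starters with prior ACEI use. Not given. Section 7.1.1 expects most starters to have had an ACEI or ARB, and cites 43% and 92.2% for the two classes combined in two external populations with reduced ejection fraction. Neither is an ACEI-only share among starters, so s is varied from 30% to 92.2% as an assumption.
- f = share of same-day cases with no prior ACEI record. Not given; taken as 0 first, then varied.
- p_all = reported proportion among all starters. Assumed to be 2% for illustration.

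**Formula.** With m same-day cases, p_all = m / N. The switchers number s × N and contribute (1 − f) × m cases. Hence

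p_switch = (1 − f) × m / (s × N) = p_all × (1 − f) / s.

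**Results with f = 0.** Here m = 0.02 × 29,000 = 580.

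| s (assumed) | Switchers, s × 29,000 | 580 / switchers | Factor 1/s |
|---|---|---|---|
| 30% | 8,700 | 6.7% | 3.33 |
| 43% | 12,470 | 4.7% | 2.33 |
| 50% | 14,500 | 4.0% | 2.00 |
| 70% | 20,300 | 2.9% | 1.43 |
| 92.2% | 26,738 | 2.2% | 1.08 |

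The factor 1/s does not depend on the assumed 2%.

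**Sensitivity to f.** The factor is (1 − f) / s, which falls to 1 when f = 1 − s. At s = 50% it is 1.8 for f = 0.1, 1.4 for f = 0.3 and 1.0 for f = 0.5. At s = 92.2% it is already 0.98 for f = 0.1. The understatement therefore requires that most same-day cases have prior ACEI use, and it is fragile when nearly all starters do.

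**Between databases.** Suppose 4% of switchers have a same-day record in two databases, with s = 30% in one and 70% in the other. The planned measure reports 0.30 × 4% = 1.2% and 0.70 × 4% = 2.8%. The gap comes from the denominator alone.

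**Order of steps.** Same-day patients are excluded from all cohorts (Section 7.2.4). A proportion computed inside cohort 1 after that exclusion would be zero by construction, so it has to be taken before the exclusion. Section 7.7.1.2.1 does not say this.

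**Label.** Section 7.9 says that, because of starts before the washout is complete, "the risk of angioedema in cohort 1 may be slightly overestimated". Same-day patients are no longer in cohort 1. The remark can hold only if early starts that the same-day rule did not flag remain there, so the protocol itself implies that same-day records miss some early starts.

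**The case against.** The best defence concerns the window, and it stands. A reader might infer that counting one calendar day against a 36-hour rule is a mistake, because with a start time uniform over the day the index date covers on average only 24 / 2 = 12 of the preceding 36 hours. That arithmetic treats record dates as dose times. The databases hold prescription or fill dates, and Section 7.9 gives this as the reason for the restriction. An ACEI record the day before the start fits a properly delayed switch as well as an early one, and one the day after fits a switch back. They are not shown to be evidence of equal quality. ACEI records later in the episode measure add-on or switching, which Section 7.7.1.2.1 already summarises.

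On the denominator, the defence is that 7.7.1.2.1 calls the measure a current proposal, that detail belongs in the SAP, and that the output is descriptive and outside the objectives in Section 6. Section 3 also records PRAC/CHMP endorsement of Amendment 1, and the later logged changes leave this measure alone. A reader could approximate a switcher proportion from the planned baseline and attrition tables.

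Part of this stands: the approximation is possible, so it would be too strong to say that databases cannot be compared at all. But those tables are not planned to show how many same-day cases had prior ACEI use. The protocol also states the denominator itself rather than leaving it open, and no section aligns it with the question. Endorsement of the amendment does not show that the mismatch was noticed.

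**Conclusion.** The point holds for the denominator and, to a lesser degree, for the label. The planned proportion does not describe the population the question names. It is lower than the proportion among switchers by a factor of 1/s, about 3.3 to 1.1 over the assumed range, provided same-day cases come mainly from prior ACEI users.

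The size cannot be fixed from the protocol. A reader might want to quote one percentage by which adherence is overstated, but that would only restate an assumed s, and the effect could be small if nearly all starters had an ACEI before. Nor can the same-day figure be called a strict lower bound on true violations. A same-day record shows prescribing or supply, not intake, so some cases may be false positives. What the protocol supports is that the measure is an estimate likely to miss some early starts.

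The choice of denominator affects this descriptive output only; it changes no incidence rate or hazard ratio. It should still be corrected, because the output answers a regulator's request and the correction is nearly free.

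**What to change.** In Sections 7.7.1.2.1 and 7.10:

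1. Report the same-day proportion per database with, as main denominator, starters who have an ACEI record in the 365 days before index, excluding the index date. Restrict the numerator to the same patients. Give all starters as a secondary denominator, and show how many same-day cases had no prior ACEI record.
2. State that both proportions are calculated before the same-day exclusion of Section 7.2.4 is applied.
3. Describe the result as an estimate from co-prescription records that is likely to miss some early starts, instead of as the violation rate, and cross-refer to Section 7.9.

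A separate count of ACEI records on the preceding day is optional. If given, it should not be merged with the same-day figure.

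The cost is a few sentences and a few table rows per database. Section 7.3.3 already captures prior ACEI use in the required form, so no new extraction is needed. No clinical rule, cohort definition or other analysis changes.

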#### 7.7.1.2.2 Analyses of primary, secondary and exploratory objectives

For databases with a partial linkage to hospitalization data, the linked and unlinked subsets will be analyzed separately, to allow interpretation of additional hospital diagnoses in the analyses. This will be applied across all data analyses.

The COVID-19 pandemic has caused disruption of the health care systems from 2020 onward. In order to assess its impact on the analyses, the primary analysis will focus on the pre-COVID period, which is censored at 31 December 2019. The primary and secondary objectives (the period until the latest extraction date) will be assessed in the full study period as a sensitivity analysis.

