### Study size

Based on estimates from forecasts, approximately 29,000 sacubitril/valsartan initiators may be included in this study with an accumulated 24,000 patient-years (PYs) of sacubitril/valsartan exposure. If 132 cases of angioedema are reported, this would allow estimating an incidence rate (IR) of 5.5/1,000 PYs with a 95% confidence interval (CI) ranging from 4.6 to 6.5. Feasibility assessments will provide information about how many potential patients initiating ACEIs will possibly be included in the study.

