## 4 Milestones

**Table 4-1 PASS Study milestones**

Milestone	Planned date	Actual date
Start of data collection	Q2 2017	September 2017
End of data collection	After reaching approximately 24,000 PYs of total exposure with sacubitril/valsartan in the database(s), but latest 31 Dec 2021	NA
Interim report 1	Q1 2018	Submitted March 2018
Interim report 2	Q1 2019	Submitted March 2019
Interim report 3	Q1 2020	Submitted March 2020
Interim report 4	Q1 2021	Submitted March 2021
Interim report 5	Q1 2022	NA
Registration in the EU PAS register	After endorsement by CHMP/PRAC	16 March 2017
Final report of study results	31 December 2022	NA

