### **7.5 Study size/power calculation**

[figure not shown]
Since the primary objective of the study is to estimate the IR of angioedema and other safety events of interest with sacubitril/valsartan, [Figure 7-3](#) presents CIs expected for angioedema, the rarest of all the events, given different sample sizes. An IR of angioedema following sacubitril/valsartan was set to be 5.5/1,000 PYs, based on an IR of 2.9/1,000 PYs following

ACEI estimated via meta-analysis, using data up to 1 year from three observational retrospective cohort studies (Figure 7-5 and Table 7-9, random effect Poisson model using data from Burkhart et al 1996, Miller et al 2008, and Toh et al 2012) and set to an IR ratio sacubitril/valsartan/ACEI of 1.9, based on the results of the double-blind part of the pivotal phase III study PARADIGM (McMurray et al 2014). Figure 7-4 shows expected CIs for the hazard ratio (HR) of sacubitril/valsartan versus ACEI for angioedema (exploratory objective [see Section 6.3]) for different sample sizes. In addition to previous assumptions on sacubitril/valsartan and ACEI IRs, the same exposure for sacubitril/valsartan and ACEIs was added.

[figure not shown]
With these assumptions, it is aimed to approximately have 24,000 PY of exposure with sacubitril/valsartan, which will provide an estimated IR of 5.5/1000 PY [95% CI: 4.6-6.5], if we observe 132 angioedema cases.

**Figure 7-3**      **Examples of confidence intervals for the incidence rate of angioedema after exposure to sacubitril/valsartan**

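### The 24,000 patient-year size and its confidence interval cover exposure to the end of data collection, but the primary analysis is censored at 31 December 2019 and has no stated size of its own

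*Protocol*

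**What the plan says.** Four places fix the size by total exposure.

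- Section 7.5, which opens from the primary objective: "it is aimed to approximately have 24,000 PY of exposure with sacubitril/valsartan". This is expected to give "an estimated IR of 5.5/1000 PY [95% CI: 4.6-6.5], if we observe 132 angioedema cases".
- Abstract, Study size: "approximately 29,000 sacubitril/valsartan initiators may be included in this study with an accumulated 24,000 patient-years (PYs"), with the same cases and interval.
- Section 7.1.1: "Data collection will end when the necessary sample size of 24,000 PYs is reached", with 31 December 2021 as the outer limit whether or not the target is met.
- Table 4-1, end of data collection: "After reaching approximately 24,000 PYs of total exposure with sacubitril/valsartan in the database(s), but latest 31 Dec 2021". The abstract's milestones repeat this.

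Section 7.7.1.2.2 then sets a different window for the analysis: "the primary analysis will focus on the pre-COVID period, which is censored at 31 December 2019". The same section makes the full period a sensitivity analysis for the primary and secondary objectives.

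Table 7-1 gives the expected end of data as December 2019 for GePaRD; December 2020 for Aarhus, HSD, PHARMO and CPRD; April 2021 for ARS; and June 2021 for SIDIAP.

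**The concern.** The target and the primary analysis count different windows. Six of the seven databases have 12 to 18 months of data after the cut. That exposure helps to reach 24,000 PY and to end data collection, yet none of it can enter the primary incidence rate. Sections 7.5, 7.1.1, Table 4-1 and the abstract do not mention the cut, and no PY figure, case count or interval is given for the period to end-2019.

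At stake is how the final report will be read. Someone comparing achieved PY with 24,000 needs to know which analysis that benchmark describes. As written, the target could be reported as met on full-period exposure while the primary analysis rests on fewer PY, and the printed interval would be taken for the precision of an analysis to which it does not belong.

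**Working it through.** **1. The plan's own figure.** Section 7.5 gives a rate "based on an IR of 2.9/1,000 PYs following" ACE inhibitors and a ratio "set to an IR ratio sacubitril/valsartan/ACEI of 1.9".

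- Rate: 2.9 × 1.9 = 5.51, used as 5.5 per 1,000 PY.
- Cases: 0.0055 × 24,000 = 132.
- Exact Poisson 95% CI: lower = χ²(0.025; 264)/(2 × 24,000) and upper = χ²(0.975; 266)/(2 × 24,000), giving 4.60 to 6.52 per 1,000 PY.

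The printed 4.6-6.5 reproduces. There is no error of calculation.

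**2. What the cut removes from each database.** Let a be the months from launch to end of data (Table 7-1) and b the months from launch to December 2019. With constant exposure the share of PY lost is 1 − b/a. With use growing linearly from launch, cumulative PY grows as time squared and the share lost is 1 − (b/a)².

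| Database | a | b | Lost, constant | Lost, linear uptake |
|---|---|---|---|---|
| Aarhus | 61 | 49 | 20% | 35% |
| CPRD | 61 | 49 | 20% | 35% |
| HSD | 57 | 45 | 21% | 38% |
| PHARMO | 54 | 42 | 22% | 40% |
| ARS | 61 | 45 | 26% | 46% |
| SIDIAP | 57 | 39 | 32% | 53% |
| GePaRD | 48 | 48 | 0% | 0% |

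In total 82 of 399 database-months (21%) fall after the cut. Section 7.2.3 puts the latest data at April 2021, two months before Table 7-1's date for SIDIAP; on that date SIDIAP would lose 16 of 55 months (29%).

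**3. Pooled effect.** This depends on GePaRD's share of PY, which the protocol does not state. The only documented share is of initiators in the feasibility cohort (section 7.1.2, objective 4): 4,724 of 5,185 = 91.1%, leaving 8.9% for the other six. Assume that this share applies to PY, that 24,000 PY is the full-period total, and that the six databases weigh equally. Their mean loss is 23.4% (constant), 41.2% (linear uptake) or 54.7% (quadratic uptake, cumulative PY as time cubed).

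| Exposure pattern | Pooled loss | PY to end-2019 | Cases at 5.5/1,000 | Exact 95% CI |
|---|---|---|---|---|
| Constant | 0.089 × 23.4% = 2.1% | 23,500 | 129 | 4.59-6.53 |
| Linear uptake | 0.089 × 41.2% = 3.7% | 23,120 | 127 | 4.59-6.54 |
| Quadratic uptake | 0.089 × 54.7% = 4.9% | 22,830 | 126 | 4.58-6.55 |

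(CIs use the unrounded expected count; rounding it to whole cases moves the limits by about 0.02.)

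**4. Dependence on the assumed share.** If the six databases held 40% of PY, a figure with no source in the protocol, linear uptake would leave 24,000 × (1 − 0.40 × 0.412) ≈ 20,050 PY, about 110 cases and a CI of about 4.5-6.6. Quadratic uptake would leave about 18,750 PY, 103 cases and about 4.5-6.7. These show sensitivity and are not estimates.

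**The case against.** The case against acting is substantial.

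- **The arithmetic is sound and the effect may be negligible.** On the only documented share, the pooled interval moves by a few hundredths. This stands and limits the size of the point.
- **The size is approximate and illustrative.** The target is an aim, the interval is conditional on 132 cases, and Figure 7-3 (not shown) covers several sample sizes. No hypothesis test or decision depends on reaching 24,000 PY. This stands as to consequence. But approximation concerns how many PY there are, not which window they are counted over.
- **The stopping rule has little force left.** Its outer limit, 31 December 2021, had passed when this version was dated 22 March 2022, and the 2020-2021 data have a declared use in the sensitivity analysis. This also stands; what remains is how the benchmark is read.
- **The cut is deliberate and explained.** True, and it is not criticised here. The size statements were not aligned with it.
- **The assumed rate matters more.** Section 5.1 reports a crude 0.7 (0.4-1.1) per 1,000 PY at the fourth interim. At 0.7, 24,000 PY gives about 17 cases and a CI of about 0.4-1.1. That is a separate issue and does not reconcile the two windows.

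Two stronger readings are tempting. A reader might infer that about a fifth of the primary sample is lost, from the 21% of database-months or from a 40% share. The protocol does not support this: database-months are not PY, the database with most initiators loses none, and the 40% share is only an assumption. A reader might also infer that the primary analysis will fall short of 24,000 PY. That cannot be known either, since neither the PY to end-2019 nor the realised full-period total is given.

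**Conclusion.** The point holds as an internal inconsistency. The size, interval and end-of-collection rule describe full-period exposure, and therefore the sensitivity analysis; the primary analysis has no stated size.

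The pooled consequence is small on the available evidence: about 2-5% of PY and a CI of at most about 4.6-6.6, provided that GePaRD's 91% share of initiators carries over to PY. Larger pooled losses require a smaller GePaRD share, for which the protocol gives no basis. The effect is clearer in the per-database rates that section 7.7.1.2.2 also plans: six databases each lose 20-32% of their calendar window, or about 35-53% of PY if uptake is linear. A correction is worth making because it is cheap and the 24,000 PY will be the benchmark for the final report; it does not call the analysis itself into question.

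**What to change.** In section 7.5 and the abstract, state the cohort 1 PY available to 31 December 2019, overall and by database, with the expected cases and 95% CI, as the size of the primary analysis. Label the 24,000 PY, 132 cases and 4.6-6.5 as the size of the full-period sensitivity analysis. In section 7.1.1 and Table 4-1 (and the matching milestone in the abstract), say that the 24,000 PY rule refers to full-period exposure and that meeting it does not show that the primary analysis has reached its size.

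Simply redefining 24,000 PY as exposure to end-2019 would be less sound: the figure was set for the whole collection period, and the earlier window is closed, so any shortfall could not be made up.

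The cost is wording in these places and one tabulation of PY by calendar cut. Table 7-1 has every database reaching December 2019, so no new data are needed. The stated precision may become slightly less favourable.
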